Rationale:	The Post-traumatic Stress Disorder (PTSD) Psychopharmacology Working Group has recently called for novel, effective and efficient trauma-focused interventions and has labelled current treatment outcomes as “the Crisis in the Pharmacotherapy of Post-traumatic Stress Disorder”. MDMA-assisted psychotherapy has recently received Breakthrough Therapy designation (BTD) by the FDA for PTSD, implying that psychedelic-assisted psychotherapies may provide better outcomes for patients than the current standard of care. Psilocybin therapy with COMP360 (Compass Pathways’ proprietary synthetic psilocybin formulation) has received similar BTD for treatment-resistant depression, a condition often comorbid with PTSD. It is therefore reasonable to obtain proof of feasibility for COMP360 therapy for PTSD. If demonstrated safe and well tolerated, COMP360 therapy may offer a powerful alternative to MDMA-assisted psychotherapy in reducing PTSD symptoms.
Number of Participants:	Up to 20 participants
Objectives:	
Primary Objective
 
To assess the safety and tolerability of COMP360 administered under supportive conditions in PTSD participants 
Secondary Objectives
 
To assess the efficacy of COMP360 administered under supportive conditions in reducing PTSD symptomsTo assess the effects of COMP360 administered under supportive conditions on quality of life and participant functional impairment 
Additional Objectives
 
To assess participants subjective experience of COMP360 administered under supportive conditionsTo assess participants perceived growth and resilience after COMP360 therapyTo evaluate the impact of COMP360 on real life functional activity estimated from passive data streams collected on the Cue app on participants' mobile phonesNatural language processing on the participant narrative during the interactions with the therapist

- To assess the influence of COMP360 therapy on blood biomarkers
- To assess the influence of COMP360 therapy on brain activity

Study Design and Procedures: This is a phase II, multicentre, fixed-dose open label trial. The study population will include adult men and women outpatients, 18 years of age and older meeting Diagnostic and Statistical Manual of Mental Disorders (5th Edition; DSM-5) diagnostic criteria for PTSD after a traumatic event experienced during adulthood.

Primary Endpoint(s): The safety and tolerability endpoints include:

- AEs
- 12-lead ECGs
- Clinical laboratory tests
- Vital signs
- Suicidality measured via the C-SSRS
- BPRS+

Secondary Endpoint(s): Secondary Endpoint(s)

- Change in CAPS-5 total score from baseline
- Change in PCL-5 total score from baseline
- Change in SDS total score from baseline
- Change in EQ-5D-5L total score from baseline
- Proportion of participants with response (defined as a ≥ 15 point improvement on the CAPS-5 total score from baseline)
- Proportion of participants with remission (defined as CAPS-5 total score ≤ 20)

Additional Endpoint(s):

Additional Endpoint(s)

- Change in PACT total score from baseline
- Change in RAS total score from baseline
- 5D-ASC on day 1
- Summary of the Emotional Breakthrough Inventory (EBI) total score on day 2
- Participant acceptability of the treatment assessed via a semi-structured qualitative interview *
- Quantitative and descriptive characterisation of changes in the participant narrative as a result of treatment *
- Measures derived from the Cue app installed on the participant's smart phone *
- Changes in blood biomarkers after COMP360 therapy, as well as any relationship between biomarkers pre- and post-treatment, and clinical outcomes*

- Brain activation during fMRI tasks relating to trauma-related events and an emotional go/no-go task *

*Data from the semi-structured qualitative interview and data generated from the Cue app and the MRI and blood biomarker components of study will be assessed outside of the Clinical Study Report (CSR)

Estimand Framework

An estimand framework will not be used for this study since it is a descriptive, exploratory study.

Sample Size Determination

No formal sample size calculation has been performed for this exploratory study.

Analysis Sets

The Screening Analysis Set will consist of all participants who signed the ICF.

The Safety Analysis Set will consist of all participants who receive study drug.

The Full Analysis Set (FAS) will consist of all participants in the Safety Analysis Set who have at least one post-baseline efficacy assessment.

Hypothesis

There are no formal hypotheses being tested in this study.

Primary Endpoint Analyses

Safety will be evaluated based on AEs, ECG findings, clinical laboratory assessments, vital signs, BPRS+, and suicidality (as measured via the C-SSRS).

Secondary Endpoint Analyses

VAS	Visual Analogue Scale
WHO	World Health Organization
Worldwide	Worldwide Clinical Trials, Inc.

LIST OF PARAMETERS

Parameter Definition

Study Disposition

BMI	body mass index
CTQ	Childhood Trauma Questionnaire
DSM-5	Diagnostic and Statistical Manual of Mental Disorders, 5 th Edition
LEC-5	Life Event Checklist for DSM-5
MINI	Mini International Neuropsychiatric Interview
MSI-BPD	McClean Screening Instrument for Borderline Personality Disorder

Safety

AE	adverse event
AESI	adverse event of special interest
BPRS+	Brief Psychiatric Rating Scale – Positive Symptom Subscale
C-SSRS	Columbia-Suicide Severity Rating Scale
ECG	electrocardiogram
mDESS	Modified Discontinuation Emergent Signs and Symptoms Scale
QTcB	QT interval corrected by Bazett's formula
QTcF	QT interval corrected by Fridericia's formula
SAE	Serious Adverse Event
TEAE	treatment-emergent adverse event
TESAE	treatment-emergent serious adverse event

Efficacy

5D-ASC	Five-Dimensional Altered States of Consciousness questionnaire
CAPS-5	Clinician-Administered PTSD Scale for DSM-5
EBI	Emotional Breakthrough Inventory
EQ-5D-3L	EQ-5D 3-level version
EQ-5D-5L	EQ-5D 5-level version
PACT	Perceived Ability to Cope with Trauma
PCL-5	PTSD Checklist for DSM-5
RAS	Resilience Adult Scale
SDS	Sheehan Disability Scale

1 INTRODUCTION

This statistical analysis plan (SAP) is based on the final United Kingdom (UK) protocol (V5.0) and the final United States (US) protocol (V5.0), both dated 09 June 2023. The plan covers the tables, figures and listings (TFLs) of the study data to investigate the safety and tolerability of COMP360 administered under supportive conditions in post-traumatic stress disorder (PTSD) participants.

The SAP is prepared by Compass Pathfinder Limited (Compass). The statistical analyses and production of the outputs described in the SAP, as well as the quality check (QC), will be conducted by Worldwide Clinical Trials, Inc. (Worldwide), using SAS® Version 9.4 or later.¹ The final analyses and outputs will be approved by Compass.

Any statistical analysis details described in this document supersede any description of statistical analysis in the protocol.

2 STUDY OBJECTIVES AND ENDPOINTS

The study objectives and their corresponding endpoints are presented in Table 1.

Table 1: Study Objectives and Endpoints

Objectives	Endpoints/Variables
Primary: To assess the safety and tolerability of COMP360 administered under supportive conditions in PTSD participants	The safety and tolerability endpoints include: 
• AEs• 12-lead ECGs• Clinical laboratory tests• Vital signs• Suicidality measured via the C-SSRS• BPRS+
Secondary: 
• To assess the efficacy of COMP360 administered under supportive conditions in reducing PTSD symptoms• To assess the effects of COMP360 administered under supportive conditions on quality of life and participant functional impairment	
• Change in CAPS-5 total score from baseline• Change in PCL-5 total score from baseline• Change in SDS total score from baseline• Change in EQ-5D-5L total score from baseline• Proportion of participants with response (defined as a ≥ 15 point improvement on the CAPS-5 total score from baseline)• Proportion of participants with remission (defined as CAPS-5 total score ≤ 20)
Additional:	


• To assess participants subjective experience of COMP360 administered under supportive conditions• To assess participants perceived growth and resilience after COMP360 therapy• To evaluate the impact of COMP360 on real life functional activity estimated from passive data streams collected on the Cue app on participants' mobile phones• Natural Language Processing on the participant narrative during the interactions with the therapist• To assess the influence of COMP360 therapy on blood biomarkers• To assess the influence of COMP360 therapy on brain activity	
• Change in PACT total score from baseline• Change in RAS total score from baseline• 5D-ASC on day 1• Summary of the Emotional Breakthrough Inventory (EBI) total score on day 2• Participant acceptability of the treatment assessed via a semi-structured qualitative interview *• Quantitative and descriptive characterization of changes in the participant narrative as a result of treatment *• Measures derived from the Cue app installed on the participant's smart phone *• Changes in blood biomarkers after COMP360 therapy, as well as any relationship between biomarkers pre- and post-treatment, and clinical outcomes• Brain activation during fMRI tasks relating to trauma-related events and an emotional go/no-go task *
--	--

5D-ASC=Five-Dimensional Altered States of Consciousness; AE=adverse event; BPRS+=Brief Psychiatric Rating Scale; CAPS-5=Clinical Administered PTSD Scale for DSM-5; CSR=clinical study report; C-SSRS=Columbia-Suicide Severity Rated Scale; EBI=Emotional Breakthrough Inventory; ECG=electrocardiogram; EQ-5D-5L=5-level EQ-5D version; fMRI=functional magnetic resonance imaging; PACT=Perceived Ability to Cope with Trauma; PCL-5=PTSD Checklist for DSM-5; PTSD=post-traumatic stress disorder; RAS=Resilience Adult Scale; SAP=statistical analysis plan; SDS=Sheehan Disability Scale.

3 ESTIMAND FRAMEWORK

[figure not shown]
An estimand framework will not be used for this study since it is a descriptive, exploratory study.

4 STUDY DESIGN

4.1 Study Design

The study schematic is presented in Section 4.2 and the schedule of assessments is presented in Section 4.3, Table 2.

4.2 Study Schematic

4.3 Schedule of Assessments

Table 2: Schedule of Assessments for COMP 201

	Screening (≥2 weeks Prior COMP360)		Baseline		Time Since COMP360 Treatment							
	Screen Visit ¹	Screening Period			Day -1	Administration Session (Day 1)	Day 2	Week 1	Week 2	Week 4	Week 6	Week 12 (ET)
Allowable Window	N/A	weekly	N/A		≤ 7 days	none	± 1 day	± 1 day	± 1 day	± 3 days	± 3 days	± 7 days
Visit	1	1a, 1b, etc	2		3	4	5	6	7	8	9	10
Location Visit	Clinic	Clinic ²	Clinic		Clinic	Clinic	Clinic	Clinic	Clinic	Remote/Clinic	Remote/Clinic	Clinic
Clinical Assessments and Procedures												
Informed Consent	✓											
Medical History	✓		✓									
Inclusion/exclusion Criteria review	✓		✓									
C-SSRS ³	✓	✓	✓	✓ ⁴	✓	✓	✓	✓	✓	✓	✓	✓
MINI v7.0.2	✓											
MSI-BPD	✓											
BPRS+			✓	✓ ⁴	✓	✓	✓	✓	✓	✓	✓	✓
Semi-structured PTSD management interview			✓									
Vital signs	✓		✓	✓ ⁵	✓							
ECG	✓		✓		✓							

	Screening (≥2 weeks Prior COMP360)		Baseline		Time Since COMP360 Treatment							
	Screen Visit ¹	Screening Period			Day -1	Administration Session (Day 1)	Day 2	Week 1	Week 2	Week 4	Week 6	Week 9
Allowable Window	N/A	weekly	N/A		≤ 7 days	none	± 1 day	± 1 day	± 1 day	± 3 days	± 3 days	± 7 days
Visit	1	1a, 1b, etc	2	3	4	5	6	7	8	9	10	
Location Visit	Clinic	Clinic ²	Clinic	Clinic	Clinic	Clinic	Clinic	Clinic	Remote/Clinic	Remote/Clinic	Clinic	
Weight	✓											
Height	✓											
Urinalysis⁶	✓		✓									
Urine drug screen⁶	✓		✓		✓	✓	✓	✓	✓	✓	✓	
Urine pregnancy test⁷			✓		✓							
Serum pregnancy test⁷	✓											
Clinical Laboratory tests⁶	✓ ⁸		✓		✓			✓			✓	
Biomarkers analysis			✓ ⁹					✓			✓	
MRI scan⁹			✓ ¹⁰					✓				
Activate/deactivate Cue app⁹	✓										✓	
Prior/Concomitant Medication Review	✓	✓	✓	✓ ⁴	✓	✓	✓	✓	✓	✓	✓	

	Screening (≥2 weeks Prior COMP360)		Baseline		Time Since COMP360 Treatment							
	Screen Visit ¹	Screening Period	Day -1	Administration Session (Day 1)	Day 2	Week 1	Week 2	Week 4	Week 6	Week 9	Week 12 (ET)	
Allowable Window	N/A	weekly	N/A	≤ 7 days	none	± 1 day	± 1 day	± 1 day	± 3 days	± 3 days	± 7 days	
Visit	1	1a, 1b, etc	2	3	4	5	6	7	8	9	10	
Location Visit	Clinic	Clinic ²	Clinic	Clinic	Clinic	Clinic	Clinic	Clinic	Remote/Clinic	Remote/Clinic	Clinic	
Documentation of contraceptive method to be used ⁷	✓											
IMP administration				✓								
Preparation ¹¹		✓	✓									
Psychoeducational information ¹²		✓										
Integration					✓	✓	✓					
AEs	✓	✓	✓	✓ ⁴	✓	✓	✓	✓	✓	✓	✓	
CAPS-5			✓					✓			✓	
CTQ	✓											
Participant Completed Assessments												
PCL-5	✓		✓		✓	✓	✓	✓	✓	✓	✓	
LEC-5	✓											
mDESS ¹³		✓	✓									
EQ-5D-5L			✓					✓			✓	

	Screening (≥2 weeks Prior COMP360)		Baseline		Time Since COMP360 Treatment						
	Screen Visit ¹	Screening Period	Day -1	Administration Session (Day 1)	Day 2	Week 1	Week 2	Week 4	Week 6	Week 9	Week 12 (ET)
Allowable Window	N/A	weekly	N/A	≤ 7 days	none	± 1 day	± 1 day	± 1 day	± 3 days	± 3 days	± 7 days
Visit	1	1a, 1b, etc	2	3	4	5	6	7	8	9	10
Location Visit	Clinic	Clinic ²	Clinic	Clinic	Clinic	Clinic	Clinic	Clinic	Remote/Clinic	Remote/Clinic	Clinic
SDS			✓					✓			✓
PACT			✓					✓			✓
RAS			✓					✓			✓
EBI					✓ ¹⁴						
5D-ASC				✓ ⁴							
Semi-structured qualitative interview					✓						✓

Abbreviations: AE, adverse event; BPRS+, Brief Psychiatric Rating Scale – Positive Symptom subscale; CAPS-5, Clinician Administered PTSD Scale for DMS-5; C-SSRS, Columbia-Suicide Severity Rated Scale; CTQ, Childhood Trauma Questionnaire; EBI, Emotional Breakthrough Inventory; ECG, electrocardiogram; EQ5D-5L, EuroQoL 5 dimension 5-levels; ET, early termination; IMP, Investigational Medicinal Product; mDESS=Modified Discontinuation Emergent Signs and Symptoms scale; MRI, Magnetic Resonance Imaging; MSI-BPD, McLean Screening Instrument for Borderline Personality Disorder; LEC-5, Life Events Checklist for DSM-5; MINI, Mini International Neuropsychiatric Interview; PACT, Perceived Ability to Cope with Trauma; PCL-5, PTSD Checklist for DSM-5; SDS, Sheehan Disability Scale; 5D-ASC, Five Dimensional Altered States of Consciousness

¹ If additional visits are needed to ensure adequate time for discontinuation of prior antidepressant therapy, visits should occur weekly prior to the dosing session (V3). At subsequent screening visits (V1a, V1b, etc), medications taken and any changes in medications since the previous visit and C-SSRS will be obtained, in addition, to other assessments at the study clinician's discretion. Assessments may be performed over several days, but all scales should be completed on the same day.

² Telephone check-ins will be completed in between clinic visits.

³ The "Last 12 Months" version will be administered at screening and the "Since Last Visit" version will be administered at all other visits.

⁴ This assessment will be administered at the end of the administration session.

⁵ Body temperature and respiratory rate will be measured before and at the end of the COMP360 administration session. Blood pressure and pulse rate measurements will be collected via an automatic arm cuff, with measurements collected supine at rest, in triplicate approximately one minute apart, at 15 minutes before COMP360 administration, and at one hour, three hours and six hours after

COMP360 administration. Measurements should be collected within a ± 10 -minute time window. At the end of the COMP360 administration session, a final triplicate measurement will be taken after the participant has rested for at least five minutes in the sitting position.

⁶ See protocol Section 8.2.4 for complete list of required tests to be performed.

⁷ For women of child-bearing potential only.

⁸ Only clinical laboratory tests will be tested at this visit.

⁹ Optional components of the study.

¹⁰ Baseline MRI scan can be completed within ≤ 7 days prior to baseline visit.

¹¹ Participants will have two preparation sessions during the screening period and one on day -1.

¹² Psychoeducational information will be provided by the therapist during the preparation sessions in the screening period.

¹³ Collection starting from V1b through to Baseline for those participants requiring withdrawal from prohibited medications.

¹⁴ The EBI must be performed after integration on day 2.

4.4 Hypotheses and Treatment Comparisons

There are no formal hypotheses being tested in this study.

4.5 Multiplicity

There are no formal hypotheses being tested, so no multiplicity adjustments are needed for this study.

4.6 Sample Size Considerations

The sample size is not based on a formal statistical evaluation but is considered to be adequate to meet the objectives of the study. Approximately 20 participants are expected to be enrolled in the study.

4.7 Randomisation

Not applicable.

5 PLANNED ANALYSES

5.1 Final Analysis

The SAP will be finalised before database lock. Final data analysis will be conducted after database lock. The TFLs planned in this document will be included in the final analysis.

5.2 Interim Analysis

No interim analysis is planned for this study.

5.3 Data Safety Monitoring Board (DSMB)

An independent DSMB, composed of experts in the management of participants with the disease under study and a biostatistician, will review selected safety data at predefined intervals during the study. The primary purpose of this committee will be to review safety data for the protection of participant safety. A DSMB Charter will define the primary responsibilities of the DSMB, Compass, and Worldwide, the purpose and timing of meetings, quorum, and voting details. The Charter will also provide the procedures for confidentiality, communication, and a description of the deliverables that will be provided to and reviewed by the DSMB.

A separate DSMB SAP will define the outputs the DSMB will review.

In general, the DSMB will advise Compass and make recommendations regarding continuation of the study and any modification to the protocol or study procedures in order to protect the participants enrolled in the study.

6 ANALYSIS SETS

Table 3: Analysis Sets

Analysis Set	Definition
Screening Analysis Set	All participants who signed the ICF
Safety Analysis Set	All participants who receive study drug
Full Analysis Set (FAS)	All participants in the Safety Analysis Set

ICF: Informed consent form

The Safety Analysis Set will be used for all safety-related evaluations and study population-related evaluations.

The Full Analysis Set (FAS) will be used for all efficacy-related evaluations.

7 GENERAL CONSIDERATIONS

All TFLs will be created using SAS® version 9.4 or later.

Listings will be sorted in the following order: participant, visit, and parameter unless otherwise stated. All data will be listed.

Unless otherwise specified, “baseline” is defined as the last observed value of the parameter of interest prior to dosing. This includes values collected at both scheduled and unscheduled visits. For numerical variables, change from baseline will be calculated as the difference between the value of interest and the corresponding baseline value.

Continuous data will be summarised descriptively using n (number of observations), mean, standard deviation (SD), median, minimum, and maximum.

Categorical data will be summarised using frequency counts and percentages. The denominator for a percentage will be the total number of participants in the relevant treatment group or analysis set (N), unless otherwise specified (on some occasions, percentages may be calculated using the total number of participants with available data at a particular visit or time point as the denominator [n]).

Unscheduled visits and retests (same visit number assigned) will not be displayed in by-visit summary tables but will be included in the data listings.

All individual participant data will be listed. Listings will include scheduled, unscheduled, retest and early discontinuation data.

All medical histories, adverse events (AEs), and prior and concomitant non-drug therapy will be coded from the actual verbatim term using the Medical Dictionary for Regulatory Activities (MedDRA) version 26.1 or later.

All prior and concomitant medications will be coded using the World Health Organization (WHO) Drug Global Dictionary (Sep-2023 version or later).

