Haematology	Basophils ($10^9/L$) Basophils/Leukocytes (%) Eosinophils ($10^9/L$) Eosinophils/Leukocytes (%) Mean corpuscular haemoglobin concentration (g/L) Mean corpuscular haemoglobin (pg) Mean corpuscular volume (fL) Erythrocytes ($10^{12}/L$) Haematocrit (%) Haemoglobin (g/L) Leukocytes ($10^9/L$) Lymphocytes ($10^9/L$) Lymphocytes /Leukocytes (%) Monocytes ($10^9/L$) Monocytes/Leukocytes (%) Neutrophils ($10^9/L$) Neutrophils/Leukocytes (%) Platelets ($10^9/L$)
Chemistry	Alanine aminotransferase (ALT) (U/L) Albumin (g/L) Alkaline phosphatase (ALP) (U/L) Amylase (U/L) Aspartate aminotransferase (AST) (U/L) Bicarbonate (mmol/L) Bilirubin (direct, indirect, and total) (mg/dL) Calcium (mg/dL) Chloride (mmol/L) Creatine Kinase (U/L) Creatinine (mg/dL) Gamma-glutamyl transferase (U/L) Glucose (mg/dL) Lactate dehydrogenase (U/L) Lipase (U/L) Magnesium (mg/dL) Phosphate (mg/dL) Potassium (mmol/L) Protein total (g/L) Sodium (mmol/L) Urate (mg/dL) Urea nitrogen (mg/dL)
Urinalysis	Bilirubin Glucose Ketones Leukocytes

	Nitrite Blood Protein Specific Gravity Urobilinogen pH
--	---

The laboratory tests data will be obtained at Screening, Baseline, Day 2, Week 4, and Week 12 (Visits 1, 2, 4, 7, and 10 respectively).

8.3.3 *Vital Signs Parameters*

The full list of vital signs parameters and their units are reported below:

- Systolic blood pressure (mmHg)
- Diastolic blood pressure (mmHg)
- Pulse rate (bpm [beats per minute])
- Respiration rate (breath / min)
- Body temperature (°C)

The vital signs data will be obtained at Screening, Baseline, Day 1, and Day 2 (Visits 1, 2, 3, and 4 respectively). On COMP360 administration day (Day 1), body temperature and respiratory rate will be measured before and after COMP360 administration. Blood pressure and pulse rate will be monitored via an automatic arm cuff with measurements collected supine at rest, in triplicate approximately one minute apart, at 15 minutes before study drug administration, and one, three and, six hours after COMP360 administration. Measurements should be collected within a ± 10 -minute time window. Blood pressure measurement is to be repeated until normalised if found to be elevated at the six-hour measurement.

8.3.3.1 *Vital Signs Ranges of Clinical Importance*

Values outside the following ranges for the vital signs parameters will be considered clinically important (Table 8):

Table 8: Vital Signs Parameters Ranges of Clinical Importance

Vital Sign (Units)	Lower Limit	Upper Limit

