10.2 Laboratory Tests

Descriptive statistics of the observed values and change from baseline (continuous data) will be presented for each haematology (*Table 14.3.4.1*) and chemistry (*Table 14.3.4.2*) parameter by visit.

Shift tables will display numbers of participants with normal range shifts at baseline versus post-treatment at Day 2, Week 4, and Week 12 (*Table 14.3.4.3* and *Table 14.3.4.4* for haematology and chemistry, respectively).

Listings for haematology, chemistry, and urinalysis data (*Listing 16.2.8.1*, *Listing 16.2.8.2*, and *Listing 16.2.8.3*) will also flag values that are outside normal reference ranges or markedly abnormal findings. Clinically significant laboratory data will also be listed separately (*Listing 16.2.8.4*).

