10.3 Vital Signs

Descriptive statistics of the observed values and change from baseline on non-administration and administration visits will be presented for each parameter by visit and by timepoint on COMP360 administration day (*Table 14.3.5.1*, *Figure 14.3.5.1* [for day of dosing only]). Individual participant plots will also be produced for the observed and change from baseline values for each parameter by timepoint on COMP360 administration

day only (*Figure 14.3.5.2*). The number and percentage of participants with values outside clinically important limits, as described in Section 8.3.3.1 will be summarised by visit and timepoint on COMP360 administration day (*Table 14.3.5.2*).

All vital signs data will be listed, which will also include flagged values that are outside normal reference ranges or markedly abnormal findings (*Listing 16.2.8.7*). Clinically important vital signs values will also be listed separately (*Listing 16.2.8.8*).

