15.4 Baseline Definitions

Table 17: Baseline Definitions

Parameter	Baseline
Safety	
All	Day -1
Vital Signs	Day 1 (pre-COMP360 administration)
Efficacy	
All	Day -1

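### By-visit safety tables leave out unscheduled and retest values, and no any/worst post-dose row brings those values back into a count

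*SAP*

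**What the plan says.** The display rule is in SAP Section 7: "Unscheduled visits and retests (same visit number assigned) will not be displayed in by-visit summary tables"; they go to the listings instead. The same section adds that "Listings will include scheduled, unscheduled, retest and early discontinuation data", so nothing is lost from the data; the rule limits what is tabulated.

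The tables concerned are built on scheduled visits:

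- Laboratory (SAP 10.2, Tables 14.3.4.3 and 14.3.4.4): "Shift tables will display numbers of participants with normal range shifts at baseline versus post-treatment at Day 2, Week 4, and Week 12".
- Vital signs outside the Table 8 limits (SAP 10.3, Table 14.3.5.2): these "will be summarised by visit and timepoint on COMP360 administration" day.
- QTc categories (SAP 10.4, Table 14.3.6.3) and C-SSRS (SAP 10.5, Table 14.3.6.4): by visit.

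On baseline, SAP Section 7 takes the last value before dosing unless otherwise specified and says: "This includes values collected at both scheduled and unscheduled visits". SAP 15.4, Table 17, instead fixes baseline at Day -1, and for vital signs at "Day 1 (pre-COMP360 administration)".

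On repeats, SAP 8.3.3 says: "Blood pressure measurement is to be repeated until normalised if found to be elevated at the six-hour measurement".

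**The concern.** ECGs, laboratory tests, vital signs and C-SSRS are each named as primary endpoints (SAP Section 2, Table 1), alongside adverse events and BPRS+. A reader will take the tabulated counts as the study's answer on them. Restricting by-visit rows to scheduled data is sound, because it gives one record per participant per visit. The usual companion is a row that asks whether the participant was ever abnormal after dosing, whatever the visit type. That row is missing, so a finding seen only at an unscheduled post-dose contact appears in no count for the endpoint it belongs to. In a single-arm study of about 20 people, one participant can turn a reported zero into a non-zero incidence.

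**Working it through.** The plan gives no figure to reproduce: there is no sample size calculation, no hypothesis test and no stated rate of unscheduled assessments. The check sets the display rule against each table and against the other routes by which a value could reach a count.

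**Step 1. Which scheduled post-dose rows exist?**

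| Endpoint | Scheduled post-dose collection (SAP) | Table | Any/worst post-dose row |
|---|---|---|---|
| Laboratory | Day 2, Week 4, Week 12 (8.3.2) | 14.3.4.3, 14.3.4.4 | none |
| Vital signs | Day 1 timepoints, Day 2 (8.3.3) | 14.3.5.2 | none |
| ECG/QTcF | Day 2 only (8.3.4) | 14.3.6.3 | none |
| C-SSRS | each scheduled visit (Table 2) | 14.3.6.4 | none |

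The addendum adds CAPS-5, 5D-ASC, mDESS and concomitant medication outputs, but nothing that fills the last column. Any ECG or vital sign taken after Day 2 is unscheduled by definition and has no row to enter.

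**Step 2. Would a later scheduled assessment recover the finding?** For C-SSRS, perhaps not. After screening the since-last-visit form is used (SAP 8.3.5). If it is given at an unscheduled visit, the next scheduled form covers only the time since that visit, so a positive answer at the unscheduled visit may not recur. For ECG and vital signs after Day 2, no later scheduled assessment exists.

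**Step 3. Would the adverse event tables recover it?** In part.

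- C-SSRS ideation items 4 or 5, or any suicidal behaviour, must be reported as an AE or SAE (Protocol 8.2.1). Suicidal ideation and behaviour are also AESI categories (SAP Table 5). These cases are recovered.
- Ideation items 1 to 3 become AEs only by investigator judgment (Protocol 8.2.1). These are not reliably recovered.
- An isolated abnormal laboratory, vital-sign or ECG finding becomes an AE only if it is symptomatic, leads to discontinuation or withdrawal, needs corrective treatment, or is judged to be an AE (Protocol 11.1; laboratory changes also 11.7). An asymptomatic, untreated excursion need not be.

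**Step 4. Scale.** With N = 20 (SAP 4.6), one participant is 1/20 = 5.0 percentage points. Exact (Clopper-Pearson) 95% intervals:

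- 0/20 = 0%: upper limit 1 − 0.025^(1/20) = 16.8%
- 1/20 = 5.0%: 0.1% to 24.9%
- 2/20 = 10.0%: 1.2% to 31.7%

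The frequency of participants abnormal only at an unscheduled assessment is unknown. Under an assumed probability p per participant, the chance of at least one among 20 is 1 − (1 − p)^20:

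- p = 1%: 18%
- p = 5%: 64%
- p = 10%: 88%

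These values of p illustrate a range and are not estimates.

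**Step 5. Baseline.** Section 7 and Table 17 can give different baselines when an unscheduled pre-dose value exists. Among the five tables, this can alter the laboratory shifts and the QTcF change categories. It cannot alter counts outside fixed vital-sign limits, absolute QTcF categories or C-SSRS answers.

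**The case against.** The strongest reply is that this is ordinary practice with adequate back-up. Scheduled-only rows avoid double counting. Every unscheduled value is listed, and clinically significant laboratory values and clinically important vital signs and ECGs have separate listings (16.2.8.4, 16.2.8.8, 16.2.8.10). Twenty participants can be read case by case, and no inference depends on an extra row. All of this stands, and it limits the weight of the point. It does not close the gap, because a listing supplies no count or percentage and C-SSRS has only a full listing.

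A reader might also infer several stronger things that the documents do not support:

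- *That retests are the readings most likely to be abnormal.* The repeat rule in SAP 8.3.3 is triggered by an elevated scheduled six-hour blood pressure. That reading stays in Table 14.3.5.2; what drops out is the series taken until normal. A narrow gap remains, because that rule does not define elevated, so a repeat could be the first reading beyond the Table 8 limits.
- *That the protocol requires the repeat blood pressure.* The supplied protocol schedules Day 1 vital signs before dosing only. The rule is in the SAP, which says it is based on protocol V5.0.
- *That a blood pressure rise after six hours is invisible.* Day 2 vital signs are scheduled and tabulated. SAP Table 2 also schedules an end-of-session triplicate, although Table 16 gives it no label, which is a separate matter.
- *That these values drop out of all primary safety summaries.* AE and AESI tables are not by visit and carry no such exclusion.
- *That unscheduled values can set baseline but not outcome, tilting the tables toward normal.* Section 7 yields where something else is specified, and Table 17 specifies fixed visits. No direction of bias is shown.

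**Conclusion.** The point holds for the five by-visit tables. As planned, a participant whose only abnormal laboratory value, vital sign or QTcF, or only positive C-SSRS answer, arises at an unscheduled post-dose assessment is missing from the relevant count. It matters most for C-SSRS ideation items 1 to 3, and for ECGs and vital signs after Day 2.

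Each omitted participant shifts a reported incidence by 5 percentage points at N = 20. Whether any such participant exists cannot be told from the documents. That unscheduled visits are prompted by a clinical concern is plausible, but it is an assumption. The conclusion also assumes that the Section 7 display rule is applied as written to every table summarised by visit.

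This is a worthwhile, inexpensive improvement to safety reporting. It is not evidence that the safety results are biased.

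**What to change.** Keep the scheduled by-visit rows unchanged. Add to Tables 14.3.4.3, 14.3.4.4, 14.3.5.2, 14.3.6.3 and 14.3.6.4 one row for any/worst post-dose value, drawing on scheduled, unscheduled and repeat assessments and counting each participant once per parameter or C-SSRS category. Because the existing addendum was already written after database lock, label this row as a post-lock addition if it is made now.

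In the same change, state whether Section 7 or Table 17 governs baseline when an unscheduled pre-dose value exists.

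The cost is one derived record per participant per parameter and a small programming effort. No new data are needed, since all these values already feed the listings.
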